10.3.4. Pharmacokinetic/Pharmacodynamic Analyses	44
11. References	45

List of Tables

Table	List of Tables	Page
Table LAIF.1.	Objectives and Endpoints	18
Table LAIF.2.	Treatments Administered.....	28
Table LAIF.3.	Treatment Schedule	28

List of Figures

Figure	List of Figures	Page
Figure LAIF.1.	Study schematic.....	20
Figure LAIF.2	Timing of doses.....	29
Figure LAIF.3.	Pharmacodynamic statistical inference – graphical multiple comparisons procedure.....	43

List of Appendices

Appendix		Page
Appendix 1.	Abbreviations and Definitions	46
Appendix 2.	Clinical Laboratory Tests.....	50
Appendix 3.	Study Governance, Regulatory, and Ethical Considerations	51
Appendix 4.	Hepatic Monitoring Tests for Treatment-Emergent Abnormality	54
Appendix 5.	Blood Sampling Summary	55
Appendix 6.	Protocol Amendment H8H-MC-LAIF(a) Summary: A Phase I, Randomized, Subject- and Investigator-Blind, Placebo-Controlled, 4-Period Cross-Over Study Assessing the Duration of Effect of Lasmiditan on Simulated Driving Performance in Healthy Volunteers	56

1. Protocol Synopsis

Title of Study:

Protocol H8H-MC-LAIF: A Phase I, Randomized, Subject- and Investigator-Blind, Placebo-Controlled, 4-Period Cross-Over Study Assessing the Duration of Effect of Lasmiditan on Simulated Driving Performance in Healthy Volunteers

Rationale:

Lasmiditan is a highly selective and potent agonist at the 5-hydroxytryptamine 1F receptor and is under development as a neurally acting acute treatment for migraine. The most frequently reported adverse events (AEs) identified in the lasmiditan clinical development program are central nervous system in nature based on the mechanism of action of the drug. Due to treatment-related adverse effects of dizziness and fatigue observed in the Phase 2 clinical program, Study COL-MIG-106/H8H-MC-LAHG evaluated the impact of lasmiditan on driving performance at 90 minutes postdose. The results of this study showed impaired driving performance, but the duration of the impairment could not be estimated. The primary objective of the current study is to determine the duration of effect of lasmiditan compared to placebo on simulated driving performance in healthy subjects as measured by standard deviation of lateral position (SDLP) using the Cognitive Research Corporation Driving Simulator-MiniSim (CRCDS-MiniSim) at 8, 12, and 24 hours after dosing.

Objectives	Endpoints

Primary
 
To determine the duration of effect of acute doses of lasmiditan 100 mg and 200 mg compared to placebo on simulated driving performance in healthy subjects
	
Standard deviation of lateral position (SDLP) using the Cognitive Research Corporation Driving Simulator-MiniSim (CRCDS-MiniSim) at 8, 12, and 24 hours postdose

Secondary
 
To determine the effects of lasmiditan 100 mg, and 200 mg compared to placebo on
 
 • self-reported endpoints • performance endpoints, and • driving performance endpoints. 	
 • Sleepiness endpoint - KSS • Self-reported readiness to drive ("Right now do you feel safe to drive?") • VAS to assess subject's motivation and self-appraisal of their driving performance 
CogScreen SDC test
 
 • Number of correct responses • Response accuracy • Standard deviation of reaction time • Lane exceedance; including number, maximum, duration, and area of exceedance • Average speed, speed deviation, speed count • Excessive Ay (cornering speed threshold exceeded) • Total collisions • Divided attention (DA): correct responses, omission errors, commission errors, reaction time, standard deviation of reaction times
To evaluate the PK of lasmiditan in healthy subjects	
 • PK parameters:

following a single 100- or 200-mg oral dose of lasmiditan	 C_{\max} ,  t_{\max} , and  $AUC(0-\infty)$
---	---

Abbreviations: $AUC(0-\infty)$ = area under the concentration versus time curve from zero to infinity; C_{\max} = maximum observed drug concentration; DA = divided attention; KSS = Karolinska Sleepiness Scale; PK = pharmacokinetics; SDC = Symbol Digit Coding; t_{\max} = time of maximum observed drug concentration; VAS = Visual Analog Scale.

Summary of Study Design:

Study H8H-MC-LAIF is a multicenter, randomized, subject- and investigator-blind, active- and placebo-controlled Williams square design with 4-period (full) crossover using lasmiditan 200 mg, lasmiditan 100 mg, and diphenhydramine 50 mg. Subjects will be randomized to treatment sequences and will complete all 4 periods within that treatment sequence.

[figure not shown]
Each period will be of 3 days duration. It is anticipated that Study Periods 1, 2, 3, and 4 will commence on Study Days 1, 4, 7, and 10, respectively. For logistical reasons, the interval between periods may be extended by up to 2 days to accommodate site schedules. The minimum washout between periods is 3 days.

Screening (Visit 1) will include procedures to access subject eligibility including clinical laboratory tests, physical examination, and driving simulation training/screening. Prior to randomization, subjects will be screened for simulator sickness and will receive standardized training on the driving simulator and cognitive test battery. Screening procedures and screening assessments may be performed on different days but must be completed within 28 days before Period 1 (Visit 2). The training drives on the driving simulator must be completed no more than 21 days prior to the first dose of study drug.

Study drug or placebo will be administered by site staff during each period at 0 (Dose 1), 6 (Dose 2), and 10 (Dose 3) hours on Day 1 and at 22 hours (Dose 4) on Day 2 according to the treatment sequence assigned. Subjects will wear a blindfold when taking each dose to maintain the blind. The tablet size and shape are deemed similar enough to maintain the blind provided the subject is blindfolded. Driving assessments commence at 8, 12, and 24 hours after Dose 1.

The positive control (diphenhydramine 50 mg) is included to establish the sensitivity of the study endpoints.

Treatment Arms:

Treatment Sequences:

Subjects will be assigned and dosed with study medication (lasmiditan, diphenhydramine, or placebo) according to the treatment sequence they are randomized to. Subjects will be randomized equally into 1 of 4 treatment sequences:

Treatment Sequence	Period 1	Period 2	Period 3	Period 4
1	Placebo	Lasmiditan 100 mg	Diphenhydramine 50 mg	Lasmiditan 200 mg
2	Lasmiditan 100 mg	Lasmiditan 200 mg	Placebo	Diphenhydramine 50 mg
3	Lasmiditan 200 mg	Diphenhydramine 50 mg	Lasmiditan 100 mg	Placebo
4	Diphenhydramine 50 mg	Placebo	Lasmiditan 200 mg	Lasmiditan 100 mg

Duration of Study:

On Day -1, prior to the first dose administration (the evening of clinical research unit [CRU] admission) subjects will complete a 20-minute practice drive on the CRCDS-MiniSim and a practice trial on the CogScreen SDC test.

Period 1, Day 1 subjects will be administered Dose 1 between approximately 0700 hours (7:00 AM) and 1000 hours (10:00 AM). On subsequent dosing days of Periods 2 to 4, doses will be administered at approximately the same time of day as doses in Period 1.

Approximately 8 hours following Dose 1, subjects will perform the CogScreen SDC test, KSS, and indicate their self-perceived safety to drive. Subjects will then perform the Country Vigilance-Divided Attention driving scenario on the CRCDS-MiniSim. Upon completion of the driving scenario, subjects will be administered a VAS to assess subjects' motivation and self-appraisal of their driving performance. Subjects repeat this testing procedure at approximately 12 hours and 24 hours after Dose 1 in all dosing periods.

While resident at the CRU, lights out will occur at approximately 2300 hours (11:00 PM) every night.

Subjects will remain a resident of the CRU from admission until discharge following the completion of study assessments. Blood draws for PK will be taken at pre- and post-dose according to the schedule of activities in all periods.

The total duration of subject participation will be approximately 5 weeks (range 3 to 7 weeks).

Number of Subjects:

Approximately 72 subjects will be enrolled so that 60 healthy volunteers complete the study. This will lead to 90% or more power for testing each of the hypotheses of primary interest regarding the driving assessment endpoints.

Statistical Analysis:**Safety:**

Safety analysis will be based on all subjects enrolled who receive at least 1 dose of study medication. The safety analysis will evaluate AEs and additional safety parameters. The number and percentage of subjects experiencing at least 1 AE will be summarized by body system, preferred term, and treatment. If appropriate, AEs will also be summarized by intensity and relationship to study drug. Serious adverse events, if any, will be tabulated.

Additional safety parameters will be assessed from summaries of physical examinations, 12-lead electrocardiograms and vital signs. Hematology, chemistry, and urinalysis laboratory test results will be categorized relative to the normal ranges. The changes from baseline for each of these parameters at postdose time points will be presented. Complete listings and summary tables for all safety information including AEs, laboratory safety data, vital signs, and physical examination will be included in the study report.

Pharmacokinetics:

Pharmacokinetic parameter estimates for lasmiditan and its metabolites will be calculated using standard noncompartmental methods of analysis and summarized using descriptive statistics. Plasma concentrations of diphenhydramine will be listed and summarized using descriptive statistics.

Pharmacodynamics:

The primary endpoint, SDLP, will be analyzed using a mixed model with fixed effects for sequence, period, and treatment, and a random effect for subject within sequence for each of the driving time points. Secondary endpoints will be evaluated similarly; however, Lane Exceedance will be log transformed (more specifically $\ln[x+1]$) prior to analyses. Pairwise comparisons for readiness to drive will be analyzed using McNemar test.

Graphical analyses will be performed to explore the relationship between PK concentrations with SDLP and/or other pharmacodynamic (PD) measures. Additional analyses may be performed to further characterize the PK/PD relationship(s), if warranted.

2. Schedule of Activities

Screening		Study Informed Consent
		Medical History
		Subject Eligibility
		Weight/Height (BMI)
		Drug and Alcohol Screen (repeat alcohol screen prior to Driving Sim Training/Practice if performed at a separate visit)
		Vital Signs
		Physical Examination (may be performed through Day -1)
		Epworth Sleepiness Scale
		Clinical Laboratory Tests
		Twelve-Lead ECG
		Temperature
		Serum Pregnancy Test (females only)
		CogScreen SDC Training/Screening
		Driving Sim Training/Screening
		Simulator Sickness Questionnaire
		Concomitant Medication assessment
Day -1 (Period 1)	Admission to Clinic	
		Confirm Subject Eligibility
		Drug and Alcohol Screen
		Serum Pregnancy Test (females only)
		Vital Signs
		Directed Physical Examination (symptom driven)
		CogScreen SDC Practice
		Driving Sim Practice
		Adverse Event Assessment
		Concomitant Medication Assessment (monitor throughout study)
Day 1 (Periods 1-4)	Predose	
		Vital Signs
		Directed Physical Examination (symptom driven)
		Lasmiditan and Metabolites PK Sampling (predose)
		Diphenhydramine PK Sampling (predose)
	+0.0 h	Study Drug Administration (Dose 1)
	+0.5 h	Lasmiditan and Metabolites PK Sample ^a
	+1.0 h	
		Lasmiditan and Metabolites PK Sample ^a
		Breakfast
	+1.5 h	Lasmiditan and Metabolites PK Sample ^a
	+2.0 h	Vital Signs/Lasmiditan and Metabolites PK Sample ^a
	+3.0 h	Lasmiditan and Metabolites PK Sample ^a
	+4.0 h	
		Vital Signs/Lasmiditan and Metabolites PK Sample ^a
		Lunch
	+6.0 h	

		Lasmiditan and Metabolites PK Sample ^a
		Study Drug Administration (Dose 2)
+8.0 h		
		KSS ^b
		Adverse Event Assessment ^b
		CogScreen SDC Test ^b
		Self-Perceived Questionnaire (safe to drive)
		Lasmiditan and Metabolites PK Sample ^a
		Diphenhydramine PK Sample ^a
		CVDA Drive
		VAS (immediately after drive)
+10.0 h		
		Lasmiditan and Metabolites PK Sample ^a
		Study Drug Administration (Dose 3)
+11.0 h		Dinner
+12.0 h		
		KSS ^b
		Adverse Event Assessment ^b
		CogScreen SDC Test ^b
		Self-Perceived Questionnaire (safe to drive)
		Lasmiditan and Metabolites PK Sample ^a
		Diphenhydramine PK Sample ^a
		CVDA Drive
		VAS (immediately after drive)
Day 2 (Periods 1-4)	+22 h	Study Drug Administration (Dose 4)
	+23 h	Breakfast
	+24 h	
		KSS ^b
		Adverse Event Assessment ^b
		CogScreen SDC Test ^b
		Self-Perceived Questionnaire (safe to drive)
		Lasmiditan and Metabolites PK Sample ^a
		Diphenhydramine PK Sample ^a
		CVDA Drive
		VAS (immediately after drive)
	+36 h	Lasmiditan and Metabolites PK Sample ^a
Day 3 (Periods 1-4)	+48 h	Lasmiditan and Metabolites PK Sample ^a
Discharge (Day 3, Period 4)	Discharge from Clinical Unit	
		Vital Signs
		Physical Examination
		Clinical Laboratory Tests
		Adverse Event Assessment
		Concomitant Medication Assessment
Early Discontinuation		
		Vital Signs

		Physical Examination
		Clinical Laboratory Tests
		Twelve-Lead ECG
		Urinalysis Samples
		Serum Pregnancy Test (females only)
		Adverse Event Assessment
		Concomitant Medication assessment
Within 5 to 9 days after Discharge	Follow-up	
		Vital Signs
		Physical Examination
		Clinical Laboratory Tests
		Twelve-Lead ECG
		Urinalysis Samples
		Serum Pregnancy Test (females only)
		Adverse Event Assessment
		Concomitant Medication Assessment

Abbreviations: BMI = body mass index; CVDA = Country Vigilance-Divided Attention; ECG = electrocardiogram; h = hours, KSS = Karolinska Sleepiness Scale; PK = pharmacokinetic; SDC = Symbol Digit Coding; VAS = Visual Analog Scale.

- a Pharmacokinetic and pharmacodynamic sampling times are given as targets to be achieved within reasonable limits. For PK sampling scheduled prior to driving assessments, the sampling window should be within -5 min to avoid conflict with driving assessment. Otherwise, the standard PK sampling windows: predose: -15 minutes; >0 to 2 hours postdose: ±5 minutes; 2.5 to 6 hours postdose: ±10 minutes; 7 to 12 hours postdose: ±20 minutes; >12 hours postdose: ±30 minutes. The samples will be taken as per schedule to maintain the blind but samples will be analyzed according to the randomization table.
- b This accompanying driving assessment procedure should occur within -30 minutes before the scheduled CVDA drive targeted for this sampling time

3. Introduction

Lasmiditan is being developed by Eli Lilly and Company (Lilly) for the acute treatment of migraine attacks with or without aura in adults. This molecule has been developed by Lilly as LY573144 and by CoLucid Pharmaceuticals, Inc. as COL-144 under the Investigational New Drug application 103420. Full details of lasmiditan's preclinical and clinical safety and tolerability information are contained in the Investigator's Brochure (IB).

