5.4. Scientific Rationale for Study Design

Subjects will enter the CRU on Day -1. For the duration of the 4-period study, subjects will remain in the CRU. Each period will be of 3 days duration. It is anticipated that Study Periods 1, 2, 3, and 4 will commence on Study Days 1, 4, 7, and 10, respectively. For logistical reasons, the interval between periods may be extended by up to 2 days to accommodate site schedules. The minimum washout between periods is 3 days. Cognitive testing and driving simulation will be conducted approximately 8, 12, and 24 hours after Dose 1 on Day 1 of each study period. These driving assessment time points are expected to provide a wide range of responses including reversal of impairment.

The study design incorporates a positive control (diphenhydramine 50 mg) to confirm assay sensitivity. Per the FDA's Evaluating Drug Effects on the Ability to Operate a Motor Vehicle: Guidance for Industry (2017), sedating antihistamines are commonly used to understand the magnitude and duration of impairment. Diphenhydramine is a well-known sedating antihistamine available over the counter in the US and has been shown to have a significant

effect on driving performance (Kay et al. 1997, 2016). Diphenhydramine will be administered no more frequently than every 4 hours per package directions, coinciding with time points 2 hours prior to each driving assessment so that the maximum cognitive and sedative effect of the positive control coincide with the initiation of the driving simulation task.

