10.1. Sample Size Determination

Approximately 72 subjects will be enrolled so that approximately 60 healthy volunteers complete this study. This study is designed to test noninferiority (NI) of lasmiditan relative to placebo, with a diphenhydramine test versus placebo to confirm the sensitivity of the simulator to detect treatment effects. The following assumptions were made in the sample size computation: (a) SD of differences between lasmiditan and placebo within subject for SDLP is approximately 9.5 cm; (b) the true difference between lasmiditan doses and placebo is 0; and (c) the NI margin is proposed to be 4.4 cm, which is the effect seen with 0.05% of BAC. Under these assumptions, a sample of 60 subjects would provide >90% power to establish NI of either dose of lasmiditan compared to placebo in terms of the primary end point, SDLP. This sample size is more than adequate to detect diphenhydramine differences, which are anticipated to exceed the NI margin, from placebo.

Subjects who are randomized but who do not complete all 4 periods during the Treatment Phase may be replaced. Replacement subjects will enter the same treatment sequence as the original subjects to complete all 4 periods.

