7. SAMPLE SIZE JUSTIFICATION

Approximately 72 subjects will be enrolled so that approximately 60 healthy volunteers complete this study. This study is designed to test noninferiority (NI) of lasmiditan relative to placebo, with a diphenhydramine test versus placebo to confirm the sensitivity of the simulator to detect treatment effects. The following assumptions were made in the sample size computation: (a) standard deviation (SD) of differences between lasmiditan and placebo within subject for standard deviation of lateral position (SDLP) is approximately 9.5 cm; (b) the true difference between lasmiditan doses and placebo is 0; and (c) the NI margin is proposed to be 4.4 cm, which is the effect seen with 0.05% of blood alcohol count. Under these assumptions, a sample of 60 subjects would provide >90% power to establish NI of either dose of lasmiditan compared to placebo in terms of the primary end point, SDLP. This sample size is more than adequate to detect diphenhydramine differences, which are anticipated to exceed the NI margin, from placebo.

Subjects who are randomized but who do not complete all 4 periods during the Treatment Phase may be replaced. Replacement subjects will enter the same treatment sequence as the original subjects to complete all 4 periods.

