9.4.3 Adjustments for Multiplicity

To address multiplicity of testing associated with 2 doses of lasmiditan versus placebo at 3 time points for the primary endpoint of SDLP, ascending doses of lasmiditan at descending time points will be interpreted in a sequential manner, starting with the 100-mg dose at 24 hours and proceeding to the 200-mg dose and earlier time points via a graphical multiple comparisons procedure, as given in the following figure (Figure LAIF 3). The value of w , the split of alpha after testing 100 mg at 24 hours, will be set to 0.95 (i.e., propagating 95% of alpha to the 100 mg 12 h end point and 5% of the alpha to the 200 mg 24 h end point, assuming the 100 mg 24 h end point is successful).

[figure not shown]

Figure LAIF.3 Pharmacodynamic statistical inference – graphical multiple comparisons procedure.

Doses of lasmiditan will be considered non-inferior to placebo at a time point if the upper 95% CI on the difference in SDLP between that dose and placebo is less than 4.4 cm.

No adjustment to alpha levels will be made for the comparison of diphenhydramine either to placebo or to lasmiditan, or for secondary endpoints or analyses. Strong control of Type I error for non-inferiority, for the primary endpoint will be at the 0.05 alpha-level (two-sided).

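### The stated power of 90% or more for each primary hypothesis holds for one test at full alpha, not for the six-hypothesis testing graph in the SAP

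*Protocol*

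**What the plan says.** The synopsis (Number of Subjects) makes the broad claim: "This will lead to 90% or more power for testing each of the hypotheses of primary interest regarding the driving assessment endpoints". Protocol 10.1 and SAP 7 give the calculation behind it in the same terms: "a sample of 60 subjects would provide >90% power to establish NI of either dose of lasmiditan compared to placebo". The inputs are in protocol 10.1: "Approximately 72 subjects will be enrolled so that approximately 60 healthy volunteers complete this study"; "SD of differences between lasmiditan and placebo within subject for SDLP is approximately 9.5 cm"; "the true difference between lasmiditan doses and placebo is 0"; "the NI margin is proposed to be 4.4 cm". Neither section mentions time point, order of testing or division of alpha.

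The primary family is two doses at three drives, so six hypotheses. Protocol 10.3.3.1 orders them in a graphical procedure that begins with 100 mg at 24 h, and leaves the split w to the SAP. SAP 9.4.3 sets w = 0.95. After the first success, 95% of alpha goes to 100 mg at 12 h and "5% of the alpha to the 200 mg 24 h end point". The later steps are in Figure LAIF.3, which this review could not see. SAP 9.4.3 claims strong Type I error control at two-sided 0.05 for this family. It also states the noninferiority rule with an upper 95% limit below 4.4 cm at any dose and time point. SAP 11, which lists changes from the protocol analyses, records no revision of power.

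**The concern.** Power depends on the alpha at which a hypothesis is tested and on whether it is reached at all. The power paragraph appears to have been written for one comparison and carried unchanged into an SAP that had by then fixed an ordered procedure giving 200 mg at 24 h one twentieth of the alpha on its first pass.

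The trial asks how long the effect on driving lasts, and protocol 5.5 names 200 mg as the anticipated highest recommended dose. If 200 mg fails at a drive, readers will weigh that failure against the stated power. A figure of 90% or more for each hypothesis would lead them to read more into a failure than the design supports.

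**Working it through.** **Inputs.** From protocol 10.1 and SAP 7: n = 60, SD = 9.5 cm, margin 4.4 cm, true difference 0. From SAP 9.4.3: family alpha 0.05 two-sided (0.025 one-sided for noninferiority), first test 100 mg at 24 h, w = 0.95.

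**Step 1: reproduce the plan's figure.** Standard error = 9.5/√60 = 1.226 cm. Noncentrality = 4.4/1.226 = 3.588. At one-sided 0.025:
- Normal: Φ(3.588 − 1.960) = 94.8%.
- Noncentral t, 59 df: 94.2%.

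The stated figure is confirmed for one test at full alpha with no precondition. Under the SAP, only 100 mg at 24 h is tested that way.

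**Step 2: the two second-step tests at their first-pass alpha.**
- 100 mg at 12 h: two-sided 0.95 × 0.05 = 0.0475 (one-sided 0.02375). Power is 93.9% (t, 59 df).
- 200 mg at 24 h: two-sided 0.05 × 0.05 = 0.0025 (one-sided 0.00125). Normal: Φ(3.588 − 3.023) = 71.4%. Noncentral t: 66.5% with 59 df, about 70% with 174 df (240 observations less 60 subjects, 3 period and 3 treatment terms).

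For scale, 90% power at one-sided 0.00125 would take 91 completers (t) or 87 (normal). If all 72 enrolled subjects completed, power would be 78% (t) or 82% (normal).

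**Step 3: include the requirement that 100 mg at 24 h succeeds first.** If the tests were independent:
- 100 mg at 12 h: 0.942 × 0.939 = 88%.
- 200 mg at 24 h, first pass: 0.942 × 0.665 = 63%.

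Positive correlation raises these to at most about 92% and 67% in the simulations.

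**Step 4: the whole graph, under assumptions.** The later edges and the correlations between doses and drives are not in the available text, so both were assumed. Five graphs with w = 0.95 were simulated (30,000 trials, paired t-tests, true difference 0 throughout). Two of them, in % power:

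| Graph | Correlation (dose / time) | 100 mg 24 h | 100 mg 12 h | 100 mg 8 h | 200 mg 24 h | 200 mg 12 h | 200 mg 8 h |
|---|---|---|---|---|---|---|---|
| Two chains, no recycling | 0.5 / 0 | 94.0 | 88.4 | 83.1 | 64.8 | 43.2 | 28.7 |
| Two chains, no recycling | 0.8 / 0.8 | 94.0 | 90.8 | 88.8 | 65.4 | 55.9 | 50.8 |
| Two chains, no recycling | 0.9 / 0.95 | 94.1 | 92.4 | 91.4 | 66.6 | 61.9 | 59.3 |
| 100 mg chain recycles to 200 mg 24 h | 0.5 / 0 | 94.0 | 88.4 | 83.1 | 87.0 | 79.3 | 73.4 |
| 100 mg chain recycles to 200 mg 24 h | 0.8 / 0.8 | 94.0 | 90.8 | 88.8 | 88.0 | 85.6 | 84.2 |
| 100 mg chain recycles to 200 mg 24 h | 0.9 / 0.95 | 94.1 | 92.4 | 91.4 | 90.0 | 89.3 | 88.8 |

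Across all five graphs, four or five of the six hypotheses were below 90% for correlations up to 0.8, and two or three at 0.9 / 0.95. Final power for 200 mg at 24 h was about 63–67% without recycling and about 85–91% with it.

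**The case against.** The strongest reply is that nothing has been miscalculated. The inputs give more than 90%, and power for each hypothesis can be read as power of each test taken alone. The protocol also could not have used w, because it left that value to the SAP. Both points stand as far as they go: this is a power statement that was not updated, not a slip in arithmetic. They do not rescue the sentence, because under the SAP five of the six hypotheses are never tested alone at full alpha.

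A second reply is that the noninferiority rule is written with a 95% limit everywhere, and on that rule each comparison has about 94% power. But applying a fixed 95% limit regardless of the graph would discard the split and ordering on which SAP 9.4.3 rests its claim of strong control. The plan cannot have both.

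Three stronger readings are tempting, and the documents do not support them:
- A reader might infer that most of the six hypotheses are below 90%. That held in every assumed graph with correlations up to 0.8 but not in all graphs at 0.9 / 0.95, and neither the later edges nor the correlations can be read from the available text.
- A reader might take 66% as the final power for 200 mg at 24 h. It is the chance at the first-pass alpha only, and recycling could lift the final figure to about 85–91%.
- A reader might argue that a zero difference is itself implausible, since protocol 5.4 says: "These driving assessment time points are expected to provide a wide range of responses including reversal of impairment". That section gives no size for any residual effect, and the zero is an openly stated assumption. The present point does not depend on it.

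**Conclusion.** The claim of 90% or more for each primary hypothesis does not hold under the plan's own testing procedure. What is firm from the text alone is about 94% for 100 mg at 24 h, and about 66–71% for 200 mg at 24 h at its first-pass alpha (63–67% by t once success at 100 mg 24 h is required).

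Beyond that the size depends on the unseen figure. The claim about each hypothesis failed in every scenario tried. In the most favourable one (recycling with correlations of 0.9 and 0.95), the shortfall was only about one percentage point, on two 200 mg hypotheses. Without recycling it was more than 20 points for all three 200 mg hypotheses.

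All figures assume 60 completers, SD 9.5 cm and a true difference of 0 at every dose and drive. The simulations use paired t-tests with 59 df, so the planned mixed model could shift them slightly.

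**What to change.** In the synopsis, protocol 10.1 and SAP 7, say that the figure above 90% (about 94%) is for one test at full alpha, which under the graph means 100 mg at 24 h. Replace the statements about each hypothesis and about either dose with a short table of power per hypothesis, simulated under the actual Figure LAIF.3 with w = 0.95, and state the correlations assumed between doses and between drives.

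In protocol 10.3.3.1 and SAP 9.4.3, state that the upper limit used for a noninferiority decision has the confidence level matching the alpha the graph has allocated to that hypothesis at that step. On the first pass that is a 99.75% interval for 200 mg at 24 h (1 − 0.0025) and a 95.25% interval for 100 mg at 12 h (1 − 0.0475).

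The cost is a few reworded sentences and one simulation. The stated power becomes less favourable. No extra subjects are needed, and neither the graph nor w has to change.
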